9.0 Local Recruitment Methods

9.1 Recruitment Methods: Recruitment Process: Individuals consented are those already being seen by physical therapists at UMMC, Fairview as a part of standard practice. Physical therapy delivery will either involve or not involve the Moveo XP platform system, if individuals consent to participate and based on Group assignment (A or B).

9.2 Identification of Potential Participants: Standard practice includes a physician order for inpatient physical therapy for all individuals undergoing ECMO, as well as initial medical sedation. Most of those receiving ECMO are at least partially medically sedated at the time of physical therapy initiation. Only physical therapists who are specialty-trained ICU therapists and who are a part of this project will be working with this group of patients.

Any individual who meets inclusion criteria will be considered for participation, pending their ability to follow 3/3 one-step commands, as is outlined in the ECMO Mobility Protocol listed previously. Patients will be able to self-consent once sedation is reduced. After consent, individuals will be placed into either Group A or B and progress through the protocol. Group assignments will be determined based on 24 subjects, with the number 24 put into a random letter sequence generator prior to subject recruitment.

PROTOCOL TITLE: The Impact of Lower Extremity Weight-Bearing Leg Exercise During the Pre-Ambulation Phase of Individuals Undergoing Extracorporeal Membrane Oxygenation (ECMO)

VERSION DATE: 11/28/16

- Physical therapists working at Fairview have legitimate access to records as a part of their employment. The off-site PI will only have access to de-identified data, not medical records.
- The physical therapist assigned to a given patient will initiate contact with patients (potential subjects).

9.3 Recruitment Materials: No recruitment materials are needed.

9.4 Payment: There is no funding or payment associated with any part of this study.

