15.0 Compensation for Research-Related Injury

15.1 Compensation for Research-Related Injury: N/A

15.2 Contract Language: N/A

16.0 Consent Process

16.1 Consent Process (when consent will be obtained): Once subjects are removed from sedation and able to follow 3/3 one-step commands.

- Consent will occur in the hospital room of the subject. There will be no waiting period between initial consent and initiation of study.
- Ongoing verbal consent to activity will be addressed daily, when the therapist approaches a subject for scheduled therapy.
- Consent will be obtained via pre-approved form.

16.2 Non English-Speaking Participants: Any non-English speaking individual who is being treated by a physical therapist and who is undergoing ECMO treatment would be eligible for consent. As advised by IRB, a line on the consent form indicating who facilitated consent in the case of a non-English speaker, has been added.

PROTOCOL TITLE: The Impact of Lower Extremity Weight-Bearing Leg Exercise During the Pre-Ambulation Phase of Individuals Undergoing Extracorporeal Membrane Oxygenation (ECMO)
VERSION DATE: 11/28/16

16.3 Participants Who Are Not Yet Adults (infants, children, teenagers under 18 years of age): N/A

16.4 Cognitively Impaired Adults, or adults with fluctuating or diminished capacity to consent: N/A

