Aim 1: To determine if closed-chain leg exercise decreases the time to initial ambulation. *We hypothesize* that adding leg exercise will decrease time to ambulation.

Aim 2: To determine the impact of closed chain leg exercise on functional ability. *We hypothesize* that adding leg exercise will improve functional outcomes when added to an existing early mobilization program.

Aim 3: To determine the effect of closed chain leg exercise on hospital outcomes. *We hypothesize* that hospital related outcomes will improve when leg exercise is added to an existing early mobilization program.

Research Design & Methods

This initial pilot study will be conducted at the University of Minnesota Medical Center (UMMC), Fairview, and will involve 10 participants in each of the two groups (A and B). To account for attrition, 24 total subjects will be recruited; 12 per group. Approximately 3-5 patients are admitted to UMMC each month who are undergoing ECMO and could be considered for study inclusion. The study will be conducted with a goal endpoint of 1-year. Men and women aged 18-70 years old with refractory respiratory failure who are undergoing ECMO will participate over the duration of their ECMO treatment and hospitalization.

Recruitment and Consent

Standard practice includes a physician order for inpatient physical therapy for all individuals undergoing ECMO, as well as initial medical sedation. Most of those receiving ECMO are at least partially medically sedated at the time of physical therapy initiation. Only physical therapists who are specialty-trained ICU therapists and who are a part of this project will be working with this group of patients.

Any individual who meets inclusion criteria will be considered for participation, pending their ability to follow 3/3 one-step commands, as is outlined in the ECMO Mobility Protocol listed previously. Patients will be able to self-consent once sedation is reduced. After consent, individuals will be placed into either Group A or B and progress through the protocol. Group assignments will be determined based on 24 subjects, with the number 24 put into a random letter sequence generator prior to subject recruitment.

Inclusion Criteria

- Men and women 18-70 years old with refractory respiratory failure undergoing ECMO at the University of Minnesota Medical Center, Fairview.
- Able to follow 3 out of 3 one-step commands via protocol.
- Active Inpatient Physical Therapy Referral.

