- ECMO delivery is veno-venous with internal jugular catheter.

Exclusion Criteria

- Femoral catheter of any kind present.
- Veno-arterial ECMO setup.
- Sedation such that self-consent is not attainable.
- Medical instability, as determined by primary critical care physician.

Overview of Protocol for Aims 1-3:

Participants in either Group A (closed chain leg exercise group) or B (open chain exercise group) will progress through the established ECMO protocol led by their physical therapist. Participating therapists have extensive experience in working with patients on the Moveo who are in the ICU. Subjects will be assisted in the supine position from their bed to the Moveo device via a lateral transfer across a slide board to facilitate ease of movement.

Those in Group A will participate in leg exercise on the Moveo during item 4d of the ECMO protocol, whereby those in Group B will complete standard exercise as listed in item 4d. Group A participants will use the Moveo until subjective report of leg fatigue. Participants will self-select the pace of their leg exercise and the primary therapist will determine guidelines for percent of body weight lifted in accordance with standard practice physical therapy. Subjects will complete 1-4 sets of up to 25 reps of the squat exercise with 2 minutes of rest between each set. Subjects will receive physical therapy 5 days/week regardless of randomization into Group A or Group B.

Data Collection for Aims 1-3: Data will be collected on Day 0 (physical therapy evaluation day), Day 5, Day 10, Day 15, Day 20, Day 30, Day 45 (if applicable), and Day of discharge. Data collected will be categorized as specific to Aim 1 (time from initial physical therapy evaluation to initial ambulation), Aim 2 (functional outcomes) and Aim 3 (hospital outcomes). Recording of physiological data including heart rate (HR), blood pressure (BP), oxygen saturation (O2), and respiratory rate (RR) will be completed by trained physical therapists involved in the protocol at the onset of, and 1-minute post-conclusion of each therapy session. Therapy sessions are to be delivered at a frequency of five sessions per week.

- Functional Outcomes

- Leg strength as assessed by primary therapist via manual muscle test, using the Medical Research Council Sum Score (MRC Score)
- Grip strength, as assessed by hand dynamometer, completed by primary therapist

- 30-second sit to stand, completed by primary therapist

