 - Richmond Agitation and Sedation Scale (RASS), as completed in medical record by primary nurse
 - Functional Status Score for the Intensive Care Unit (FSS-ICU)
- Hospital Outcomes (data extraction from medical record)
 - Hospital days
 - Intensive care unit days
 - Days on ECMO
 - Days on mechanical ventilation
 - Length of time from physical therapy evaluation to initial ambulation
 - Discharge disposition- assigned a number for statistical analysis
 - Home (1)
 - Home with assistance (2)
 - Home with home therapy (3)
 - Home with outpatient therapy (4)
 - Transitional Care Unit (5)
 - Acute Inpatient Rehabilitation (6)
 - Long-term acute care hospital (7)
 - Long-term care setting (8)
 - Transfer to outside hospital (9)
- Physiological Monitoring: Monitoring physical therapists have extensive experience in mobilizing patients in the ICU, including those with arterial lines and on ventilation, as is standard practice for ICU therapy.
 - Respiratory rate (RR) via Drager Ventilators
 - Evita Series or Infinity Series
 - Oxygen (SpO2) and heart rate (HR)
 - Spacelabs Ultraview SL2700 (regular monitor)
 - Spacelabs Ultraview SL (portable monitor)
 - Blood Pressure (BP) via manual cuff or arterial line
 - Spacelabs Ultraview SL2700 or SL

Statistical Considerations

Physiological data (HR, BP, O2, RR) will be recorded throughout the study and analyzed between Groups A and B. Functional and Hospital outcomes will be analyzed to compare group differences at each of the data collection days (0, 5, 10, 15, 20, 30, 45, day of discharge).

Data will be analyzed at the University of Minnesota using the Statistical Package for Social Sciences (SPSS) software program. Test for normality will be completed via a paired t-test for parametric data and via Wilcoxon Rank Sum Test for non-parametric data.

Aim 1: Leg exercise on the Moveo will decrease time to initial ambulation.

- A paired t-test will be used to evaluate time to ambulation in Group A as compared to Group B.

Aim 2: Leg exercise on the Moveo will improve functional outcomes.

- There are 2 primary factors to assess, Group A and B, as well as the impact across time. To assess both factors, repeated measures ANOVA will be used.

Aim 3: Leg exercise on the Moveo will improve hospital outcomes.

- All hospital outcomes, except for discharge disposition, can be assessed between Group A and Group B by a paired t-test.
- Discharge disposition, categorical data, will be analyzed via Chi-Square test.

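### Day 0 is compared between groups as an outcome day, although for most patients it falls before group placement; the functional outcomes should use a pre-assignment value as a baseline covariate instead

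*Combined protocol and SAP*

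**What the plan says.** In the Project Proposal, Statistical Considerations plans to compare functional and hospital outcomes between groups "at each of the data collection days (0, 5, 10, 15, 20, 30, 45, day of discharge", so the list of days begins with 0. Data Collection for Aims 1-3 defines the first of these: "Data will be collected on Day 0 (physical therapy evaluation day".

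The timing of consent and assignment is given in other places:
- Section 9.1 of the local protocol: "Individuals consented are those already being seen by physical therapists at UMMC, Fairview as a part of standard practice".
- Recruitment and Consent: "Most of those receiving ECMO are at least partially medically sedated at the time of physical therapy initiation".
- Section 16.1, on when consent is taken: "Once subjects are removed from sedation and able to follow 3/3 one-step commands".
- Recruitment and Consent again: "After consent, individuals will be placed into either Group A or B and progress through the protocol".

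For Aim 2 the plan names two factors, group and time, and a repeated measures ANOVA. It does not say which days enter the ANOVA and does not name the interaction. No section defines a baseline, a change from baseline or a baseline covariate.

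**The concern.** A value measured before any assigned exercise cannot have been affected by that exercise. If allocation is sound, a group difference in that value is chance. A test of it spends a comparison and invites a reader to treat a small p-value as a finding.

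The same value can be useful as a covariate. With about 10 patients per arm, chance differences in strength or in the FSS-ICU can be sizeable. They carry into each later by-day comparison to the extent that baseline predicts follow-up. The by-day comparisons ignore this information. In the repeated measures ANOVA, a Day 0 level with no treatment effect pulls down the group difference averaged over time.

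For the hospital outcomes the listing has no clear meaning. Total hospital days and discharge disposition have no Day 0 value.

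**Working it through.** **Timing.** Day 0 is the evaluation. Most patients are still at least partly sedated when therapy starts, consent waits until sedation is off and 3/3 commands are followed, and placement follows consent. For most patients the order is therefore evaluation, consent, placement. Group A's Moveo work belongs to the later mobilization steps, so assigned exercise does not come before consent.

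**Plan's own figure.** 2 × 12 = 24 recruited for 20 evaluable, which implies attrition of 1 − 20/24 = 16.7%. No alpha, power, effect size or SD is given, so the sample size cannot be derived from the documents.

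**Number of tests.** Five functional outcomes × 8 days = 40 by-day comparisons, of which 5 are at Day 0. Assuming 0.05 per test and independence:
- At least one false positive among the 5 Day 0 tests: 1 − 0.95^5 = 22.6%.
- Per outcome: 1 − 0.95^8 = 33.7% with 8 days and 1 − 0.95^7 = 30.2% with 7. Correlated tests would generally give less.

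**Chance imbalance.** With n = 10 per arm, the SD of the baseline difference is √(2/10) = 0.447 SD. The probability that it exceeds 0.5 SD in either direction is 2 × [1 − Φ(0.5/0.447)] = 26%. At correlation ρ = 0.5, a 0.5 SD imbalance shifts the expected later difference by 0.5 × 0.5 = 0.25 SD.

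**Single-day power.** Only n = 10 per arm comes from the plan. Assumed: effect 1 SD, two-sided 0.05, two-sample t-test, ρ from 0 to 0.7. The noncentrality is √(n/2)/√(1 − ρ²) = 2.236/√(1 − ρ²), with 17 degrees of freedom adjusted. Unadjusted it is 2.236 with 18.

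| Analysis | 1 − ρ² | 10/(1 − ρ²) | Power | Difference detectable at 80% power |
|---|---|---|---|---|
| Unadjusted | – | 10 | 56% | 1.32 SD |
| Adjusted, ρ = 0 | 1.00 | 10.0 | 56% | 1.33 SD |
| Adjusted, ρ = 0.3 | 0.91 | 11.0 | 60% | 1.27 SD |
| Adjusted, ρ = 0.5 | 0.75 | 13.3 | 68% | 1.15 SD |
| Adjusted, ρ = 0.7 | 0.51 | 19.6 | 84% | 0.95 SD |

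These figures treat the baseline means as balanced. Averaged over chance imbalance, the variance of the adjusted estimate is multiplied by about 1 + 1/(2n − 4) = 1 + 1/16 = 1.0625 for a normally distributed baseline. A simulation of 100,000 trials at each ρ gave average adjusted powers of 54%, 58%, 66% and 82%. The table is therefore optimistic by two to three points, and adjustment at ρ near 0 costs slightly more than one degree of freedom.

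**Repeated measures.** Further assumptions: equal correlation ρ between all days, and a constant 1 SD effect on the 7 later days. With the variance of one measurement set to 1:
- Group main effect over 8 days including Day 0: effect 7/8, variance (1 + 7ρ)/8.
- Mean of the 7 later days: effect 1, variance (1 + 6ρ)/7.
- Mean of the later days minus Day 0 (a group-by-time contrast): effect 1, variance (1 + 6ρ)/7 + 1 − 2ρ.
- Mean of the later days adjusted for Day 0: effect 1, variance (1 + 6ρ)/7 − ρ².

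At ρ = 0.5 the variances are 0.5625, 0.5714, 0.5714 and 0.3214.

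| ρ | Main effect with Day 0 | Later days only | Later minus Day 0 | Later days adjusted |
|---|---|---|---|---|
| 0.3 | 84% | 92% | 66% | 97% |
| 0.5 | 69% | 80% | 80% | 96% |
| 0.7 | 58% | 69% | 95% | 99% |

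Adjustment is best in every row. The single contrast is a favourable reading of the plan, because an overall group-by-time test spreads over more degrees of freedom.

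**The case against.** A reader might infer that the plan fixes Day 0 before consent and randomisation. It does not. It says that most patients, not all, are sedated when therapy starts, and section 16.1 allows no waiting period after consent. A patient already awake could be evaluated, consented and placed on one day. The Data and Safety Monitoring Plan says that participants are randomised before the study begins. That is best read as generating the list, since individual placement follows consent.

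A reader might also infer that the baseline information is thrown away. That is true of the by-day comparisons but not of Aim 2. If Day 0 is a level of time, the group-by-time term uses it, and at ρ = 0.7 that contrast beats the unadjusted later days (95% against 69%). The shortfall there is one of efficiency.

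A Day 0 difference is chance only if allocation is sound. No concealment is described, and the treating therapist makes the first contact, so selection could show up at Day 0. A descriptive table by group would reveal that without a significance test.

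The most serious objection concerns size. The correlations come from no section. Sedated patients may have missing or floor values on effort-dependent tests such as manual muscle testing, grip and sit to stand, which would push the correlation towards zero and remove the gain. This stands, and it is why the range has to start at zero. The scope is also narrow, since time to ambulation, hospital-day counts and disposition have no baseline value of their own.

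**Conclusion.** The point holds as a minor improvement to the analysis of the functional outcomes. Day 0 is explicitly a between-group comparison day, it has no baseline role, and for most patients it very probably precedes placement. Removing it cuts the functional by-day comparisons from 40 to 35 and stops it diluting the group main effect.

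The single-day gain in power ranges from nothing at correlation 0 to 28 points (56% to 84%) at 0.7. It rests on an assumed 1 SD effect, two-sided 0.05 and a correlation that the documents do not supply. The documents do not support counting on the upper end, given the state of most patients on Day 0. Nor do they support calling the unadjusted comparisons biased in general: they are off target only conditional on a chance imbalance that has occurred.

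**What to change.** In Statistical Considerations:
1. Remove Day 0 from the between-group tests, along with any other scheduled visit that falls before a patient's first assigned session. Days are counted from the evaluation, so in a patient who wakes slowly Day 5 or later could also precede assignment.
2. Define baseline by one rule: the last scheduled value already recorded before the first assigned session.
3. Report baseline by group descriptively, without p-values, including how many values are missing or at the floor.
4. For Aim 2, analyse the post-assignment visits with ANCOVA, or with a mixed model, adjusted for that baseline. State in advance how a missing baseline is handled.
5. Leave Aim 1 and the hospital outcomes out of this change, and drop the by-day wording for hospital outcomes that have no value on a given day.

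This is a change of wording and needs no new bedside measurement, although the date of the first assigned session must be recorded. The statistical price is one degree of freedom plus a small loss if baseline turns out to be uninformative. Missing or floor baseline values in sedated patients will limit the benefit.

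### A pilot of 10 per group with no effect-size basis plans only significance tests for its three aims, with no group difference or confidence interval as a planned result

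*Combined protocol and SAP*

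**What the plan says.** The Project Proposal, under Research Design & Methods, states: "This initial pilot study will be conducted at the University of Minnesota Medical Center (UMMC), Fairview". The target is 10 patients per group. It then adds: "To account for attrition, 24 total subjects will be recruited; 12 per group". The only figures beside these are the monthly ECMO admissions and a one-year goal. No effect size, SD, significance level or power is given anywhere.

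Under Specific Aims, Aim 1 is worded "To determine if closed-chain leg exercise decreases the time to initial ambulation". Aims 2 and 3 speak of determining an impact and an effect. All three carry a hypothesis that the added exercise will help.

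The Statistical Considerations repeat each hypothesis as an assertion, for example "Aim 1: Leg exercise on the Moveo will decrease time to initial ambulation", and then name a method:
- Aim 1: "A paired t-test will be used to evaluate time to ambulation in Group A as compared to Group B".
- Aim 2: repeated measures ANOVA.
- Aim 3: a paired t-test for every hospital outcome except discharge disposition, which gets a chi-square test.

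The section also says that outcomes will be analyzed to compare the groups at each collection day. It plans no effect estimate, confidence interval, per-group spread or proportion walking, and says nothing on how a non-significant result will be read.

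**The concern.** A pilot of this size can supply a rough group difference, its spread, and the proportion of patients who reach ambulation. Those are the figures needed to plan the next trial, and none is a planned result. What is planned is a set of tests that a sample of 20 to 24 can rarely answer.

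The risk runs both ways. A non-significant test could be taken as evidence that the Moveo exercise does not help when the data are compatible with a large benefit. A significant one needs a large observed difference, which will tend to overstate a moderate true effect.

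**Working it through.** **Inputs from the documents.** 10 evaluable patients per group; 12 per group recruited, 24 in total; two randomized groups.

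**Assumptions, because the documents give none.** Significance level 5%, shown two-sided and, since the hypotheses are directional, one-sided. True differences of 0.5 SD (moderate) and 0.8 SD. A t-test for two independent groups.

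**The plan's own figure.** The 10 per group cannot be reproduced from a power formula. Only the attrition step can be checked: 2 × 12 = 24, and (12 − 10)/12 = 16.7% implied loss. That step is consistent.

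**Power.** Noncentral t with 2n − 2 degrees of freedom and noncentrality d × √(n/2). At n = 10 this is 0.5 × √5 = 1.12 and 0.8 × √5 = 1.79. At n = 12 it is 0.5 × √6 = 1.22 and 0.8 × √6 = 1.96.

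| True difference | n per group | Two-sided 5% | One-sided 5% |
|---|---|---|---|
| 0.5 SD | 10 | 18.5% | 28.5% |
| 0.5 SD | 12 | 21.6% | 32.4% |
| 0.8 SD | 10 | 39.5% | 53.0% |
| 0.8 SD | 12 | 46.6% | 60.0% |

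A true 0.5 SD benefit would therefore be non-significant in 78.4% to 81.5% of such trials two-sided, or 67.6% to 71.5% one-sided. At 0.8 SD the figures are 53.4% to 60.5% two-sided and 40.0% to 47.0% one-sided. Two-sided power of 80% is reached only at a true difference of 1.32 SD (n = 10) or 1.20 SD (n = 12).

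**Interval width.** Half-width = t(0.975, 2n − 2) × √(2/n), in SD units.
- n = 10: 2.101 × 0.447 = 0.94 SD.
- n = 12: 2.074 × 0.408 = 0.85 SD.

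An observed benefit of 0.5 SD with 10 per group would have an interval of 0.5 ± 0.94, or −0.44 to +1.44 SD. Two-sided significance at n = 10 needs an observed difference above about 0.94 pooled SD, which is 0.94/0.5 = 1.9 times a true 0.5 SD effect.

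**Variants.** The paired t-test as written, with no correlation within arbitrary pairs, gives power of 17.1% (n = 10) and 20.1% (n = 12) at 0.5 SD, two-sided. A time-to-event approximation in which every patient walks gives 14.6% (20 events) and 16.7% (24 events) for a rate ratio of 1.5, and 34.1% and 39.7% for a ratio of 2.0.

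**Reach.** The t-test figures describe Aim 1 and the day counts in Aim 3. They do not describe the ANOVA, whose power depends on within-patient correlation and missing visits that are not given, nor the chi-square test. For disposition, 20 patients over nine categories and two groups is 20/18 = 1.1 patients per cell on average.

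**The case against.** Three points on the other side stand.

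- **A pilot need not be powered.** This is right. A reader might infer that the trial is too small and should be enlarged, but the documents present it as a pilot and its size is not the fault.
- **The framing is partly exploratory.** Section 1.1 and the opening of the Specific Aims both say the purpose is to explore, and the Background adds safety and feasibility. Only Aim 1 has the yes/no wording, and Aims 2 and 3 can be read as estimation. A reader might infer that all three are set up as verdicts on efficacy. The aims do not support that, although their hypotheses are directional and the analysis section restates them as assertions.
- **No decision rule is written.** A reader might infer that each aim stands or falls on a p-value and that a null result will be reported as no difference. The documents set no threshold and no such rule. Naming a test does not forbid reporting the difference, and software usually prints one.

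The last point does not remove the problem. What software prints is not a commitment to report it. From a paired test on two independent groups, the printed interval would rest on arbitrary pairs. Output from the ANOVA or the chi-square test would not by itself give a group difference for each score or each disposition.

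**Conclusion.** The point holds as a gap between what a pilot of this size can support and what the plan says it will produce. Tests are the only named output, and no estimate or interval is pre-specified. Misreading a null result is a risk that the plan leaves open, not something it announces.

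For a true 0.5 SD difference, a non-significant result is the more likely outcome under every variant tried. For 0.8 SD that holds two-sided but not one-sided. An interval of about ±0.94 SD (n = 10) or ±0.85 SD (n = 12) would show the reader how much remains possible.

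The significance level, sidedness and effect sizes are assumptions. The interval widths also assume a difference in means with a value for every patient, which fails for time to ambulation if some patients never walk. The gap should be corrected before analysis; it does not prevent the study from running.

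**What to change.** Keep the sample size.

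**Specific Aims.** Reword Aim 1 to estimating the difference between groups in time to initial ambulation. Label the hypotheses of Aims 2 and 3 as exploratory.

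**Statistical Considerations.**
- Make the planned result the between-group difference with its 95% confidence interval, from an analysis for independent groups in place of the paired test.
- For each functional score, name one time point among the eight collection occasions for that difference.
- For time to ambulation, report the proportion walking in each group and use a method that keeps patients who never walk. One example is the cumulative incidence of walking, with death or discharge before walking as competing events.
- Report discharge disposition as proportions with intervals.
- Give the spread in each group for every outcome.
- Make p-values secondary, and state that a non-significant result is not evidence of no effect.

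**Cost.** The wording of two sections changes, and the time-to-ambulation analysis takes somewhat more work than a t-test. Patient procedures and the number recruited do not change. The downside is that the pilot can no longer claim that the Moveo exercise works or does not work.
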